3.2 Efficacy Analysis

3.2.1 Primary: VE against Pf malaria with symptoms

The primary efficacy analysis will be the modified Intention to Treat (mITT).

The primary efficacy analysis will be based on time to the first Pf malaria with symptoms. Entry into the risk set begins on the latter of a) 14 days after completing the primary vaccination series (V3 + 14 days) or b) 28 days after initiating treatment for a parasitemia event that was detected on or before V3 + 14 days, whichever comes later. Time-to-event is defined as the number of days between entry into the risk set and date of first *Pf malaria with symptoms*; subjects who do not experience the event by 26 weeks after V3 will be censored from the primary analysis or earlier date of last negative TBS result.

The survival patterns will be described by Kaplan-Meier curves for each arm and compared by the logrank test between two arms. The protective efficacy will be assessed from the Cox proportional hazards model with treatment arm as the regressor, and the vaccine efficacy will be estimated as one minus the hazard ratio.

As a secondary efficacy analysis, the cumulative probability of *Pf malaria with symptoms* through 26 weeks post V3 will be presented for each treatment arm and compared across arms based on Kaplan-Meier estimates along with 95% confidence intervals. This estimation accounts for right censoring and the comparison should be equivalent to Fisher's exact test in case of no censoring.

Sensitivity analyses will include an ITT and ATP analysis with entry into the risk set as with the mITT analysis, and ATP analyses with entries into the risk set at time of first vaccination and at V3.

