³ French language version uses “avec” (with) but this is interpreted in practice as “and/or” meaning that fever is not required for a diagnosis.

[figure not shown]
“adverse events (Aes)” and visits to the clinic where an AE was identified were called “AE visits.”

To address the Agency’s recommendation for selecting a parasitemia threshold, we examined the subset of data from the Community Survey study restricted to 6- to 10-year-olds living in Bancoumana, our proposed study site. This included 277 children who were seen on average 20.3 times (range: 1 to 43) totaling 5626 clinical visits. Of those, 221 children had at least one AE visit, where they were either positive for parasites or classified as having some diagnosis, including clinical malaria (“malaria”). On average, each AE child had 7.3 AE visits (range: 1 to 23). There were 21 cases where one AE visit was assigned two diagnoses. In 15 of those cases, one of the diagnoses was clinical malaria. The most common presentation of two diagnoses was malaria plus rhinitis. Thus, this dataset is appropriate to assess parasitemia thresholds and their potential impact on mis-identifying acute malaria based on symptoms that may arise from other non-malarial illnesses.

For the 277 children in the 6- to 10-year-old age group, 5990 blood smears were collected, of which 964 smears showed detectable parasitemia in 195 unique individuals. Of the 964 positive smears, 582 (60.4%) occurred without reported symptoms, 382 (39.6%) were associated with at least one symptom, 370 were reported as malaria, 10 were reported as another diagnosis, and 15 were reported as malaria + another diagnosis. Additionally, 5026 child visits were negative for parasitemia by RDT and/or smear. Of those, 4419 (87.9%) occurred without any reported symptoms, and 607 (12.1%) were associated with at least one symptom.

The association between parasitemia density (x-axis) and axillary temperature (y-axis) in the 370 AE visits (165 children) classified with a diagnosis of malaria is shown in Figure 9. Although temperature was weakly but significantly associated with parasite density in these children (Pearson R=0.18, p=0.001), many children with malaria did not have fever at both high and low parasite densities. Fever was relatively less common in these non-malaria cases. A significant number of children with no parasitemia also had fever.

Figure 9: Pattern of Fever and Parasites

[figure not shown]

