9.7 CLINICAL EVALUATIONS

Complete physical examination: (e.g., height and weight, heart rate, organ systems, or other functional abilities).

Electrocardiograms (EKGs): Electrocardiograms (12-lead ECGs) will be performed during screening and as needed throughout the study by the study site team in Mali and read by a Mali cardiologist if needed. Subjects with QT interval (QTc) > 460 ms will be excluded as AL may prolong QTc. Subjects with clinically significant abnormalities will also be excluded from the study.

Malaria blood smears: The gold standard for malaria diagnosis and evaluation of VE endpoints is the detection of malaria parasites on Giemsa-stained thick blood films. Blood smears are prepared in duplicate according to standard malaria challenge procedures and evaluated by trained study microscopists, and the results reported to the study PI. At least 0.5 μ L are scanned for the presence of malaria parasites. This method allows for detection of a parasite density of approximately 2 parasites/ μ L and early diagnosis, often before subjects become symptomatic for malaria. Slides are considered positive if at least one unambiguous *P. falciparum* parasite per slide are identified and confirmed by a second microscopist.

When venipuncture is performed, thick blood smears will be prepared from the blood remaining in the IV cannula or needle, or (at time points when no IV blood collection is planned) from a finger prick sample. The smears will be examined microscopically.

Thick blood smears will be used for diagnosis throughout the study.

Passive and active case detection: Contact information for the study clinic and principal investigator will be provided to the parent/legal guardian of all participants so they will be able to easily schedule a clinical evaluation for any symptoms of concern experienced by the study participant. Study participants are also welcome as walk-ins at the study clinic. Parents or guardians will be actively encouraged throughout the trial to report to the clinic whenever a participant is ill.

In addition, active outreach to study subjects will occur no less frequently than every two weeks during the malaria surveillance period. Parents / participants will be questioned at these visits for history of malaria symptoms including subjective fever, and body temperature will be assessed at each encounter (see Table 13).

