Based on recent data from Bancoumana, the symptomatic malaria rate under the control is very likely above 0.35 for children of age 6-10. We estimate a sample size of 120 per arm will allow reasonable power to detect the between-arm difference.

Table 15 presents the power calculation for detecting vaccine efficacy based on a two-sided log-rank test with the familywise type I error of 0.05. In the power calculation, vaccine efficacy is 1 minus the probability of *Pf malaria with symptoms* among the vaccinated divided by the probability of *Pf malaria with symptoms* among the controls. A drop-out rate of 10% is assumed.

With 240 subjects in the two arms, this study has over 80% power to detect the vaccine efficacy if the *Pf malaria with symptoms* rate is no less than 0.35 under the control and the vaccine efficacy is no less than 0.5.

In order to allow a booster study to proceed during a second transmission season if VE is 50% or greater in the first year, an additional 10% dropout rate has been assumed and 14 participants added for a total sample size of approximately 134 in each arm in the first year.

Table 15. Power calculation for plausible Pf *malaria with symptom* rates for two-sided log-rank test under type 1 error rate of alpha=0.05.

Pf malaria with symptoms rate under control	Vaccine efficacy	Power(%) (90 per arm)	Power(%) (100 per arm)	Power(%) (110 per arm)	Power(%) (120 per arm)	Power(%) (130 per arm)	Power(%) (140 per arm)
0.3	0.4	43	47	50	54	57	60
	0.5	62	66	70	74	77	80
	0.6	79	83	86	89	91	93
0.35	0.4	50	55	59	62	66	69
	0.5	70	75	79	82	85	88
	0.6	86	89	92	94	95	97
0.4	0.4	58	63	67	71	74	77
	0.5	78	82	86	88	91	93
	0.6	91	94	96	97	98	98
0.5	0.4	73	78	81	85	87	90
	0.5	90	92	95	96	97	98
	0.6	97	98	99	99	100	100
0.6	0.4	86	89	92	94	96	97
	0.5	96	98	99	99	99	100
	0.6	99	100	100	100	100	100

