3.4 Handling of missing Data

It is anticipated that some event dates required for safety analyses may be incomplete. If the event onset day is unknown, then the date will be imputed as the last date the subject could reliably be assumed to be event free (e.g., the previous study visit where the event was not reported). If the resolution day is incomplete, then the date will be imputed as the date that the event was reliably known to no longer be present.

It is anticipated that some TBS results will be missing. In those instances where one TBS is missed, the result will be imputed to be the same as the result of the next TBS. Up to three such single missing TBS will be allowed in a research subject during the 26 weeks of follow-up without disqualifying the participant from the ATP population (as long as the individual meets other requirements for ATP, such as receiving all three immunizations within the correct time windows). If there are situations where two or more consecutive TBS are missed, the result will again be imputed to be the same as the result of the next TBS, and the research subject will be included in the mITT population (as long as the individual meets other requirements for mITT, such as receiving all three immunizations). If the only TBS missed is the last, there will be no imputation, the missing data point will be ignored, and the individual may be included in the ATP population. If the two or more TBS missed are the last, there will be no imputation, the missing data points will be ignored, and the individual may be included in the mITT population. However, if more than the last two TBS are missed, the individual will not be included in proportional efficacy analyses, although may be included in time-to-event efficacy analyses.

Subjects who discontinue early or are lost to follow-up will be censored from applicable analyses at the last date where the study outcome can reliably be determined (e.g., date of last available TBS specimen without parasitemia).

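### Censoring event-free children at their last negative smear discards observed symptom-free follow-up, so Kaplan-Meier risk is inflated and VE is biased in a direction that depends on how the vaccine works

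*SAP*

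**What the plan says.** SAP 2.2 defines the primary event as a smear above 1000 parasites/µL together with fever or a history of fever, at least two listed symptoms or signs, or signs of severe malaria. SAP 3.2.1 then states that children without this event by 26 weeks after V3 "will be censored from the primary analysis or earlier date of last negative TBS result". Protocol 10.4.3 has the same sentence.

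Children who discontinue or are lost have a separate rule in SAP 3.4 and Protocol 10.4.1: they are censored at "the last date where the study outcome can reliably be determined (e.g., date of last available TBS specimen without parasitemia").

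Symptom surveillance does not depend on smear status. Protocol 9.7 says that "active outreach to study subjects will occur no less frequently than every two weeks during the malaria surveillance period", with symptom questions and a temperature reading. Routine smears are four-weekly. In children without symptoms they are reported only after surveillance ends (Protocol 5.1 and 9.7), so these children stay under observation. SAP 3.2.2 analyses Pf malaria (parasitaemia) in the same way as the symptomatic endpoint.

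**The concern.** A negative smear is the right last-known-free date for parasitaemia. It is the wrong one for an event that requires symptoms. A child with parasites and no symptoms has not had the event, is still at risk of it, and is known from the two-weekly contacts to be event-free.

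The time removed is also selected. A carrier who later falls ill with enough parasites counts as an event and keeps all follow-up, whereas a carrier who stays well loses the well time. Deleting only event-free time raises the estimated hazard and the Kaplan-Meier risk in any arm that has carriers. If the arms differ in carriage, the hazard ratio shifts too.

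The primary VE estimate and the planned cumulative-risk comparison are both affected. The listed sensitivity analyses change the population or the entry date, never the censoring rule, so the distortion would not show. Protocol 10.2 also ties a booster study to VE of 50% or more, so a shift of a few points near that value could matter.

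**Working it through.** **1. The plan's own figure.** Inputs from Protocol 10.2: "a two-sided log-rank test with the familywise type I error of 0.05"; "the symptomatic malaria rate under the control is very likely above 0.35 for children of age 6-10"; "the vaccine efficacy is no less than 0.5"; 120 per arm; 10% drop-out.

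- Evaluable per arm: 120 × 0.9 = 108. Risks: 0.35 and 0.35 × 0.5 = 0.175.
- HR = ln(0.825)/ln(0.65) = 0.447. Events = 108 × (0.35 + 0.175) = 56.7.
- Freedman: z = √56.7 × (1 − 0.447)/(1 + 0.447) − 1.96 = 0.92, so power is 82.1%, against 82% in Table 15.

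The censoring rule removes no event, so these inputs stand. The problem is the estimate, not the planned power.

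**2. One child.** Smears fall at V3 + 14, 42, 70, 98, 126, 154 and 182 days. Suppose a child is negative at day 42, then positive without symptoms at every later smear. Symptoms are assessed to day 182, but the child is censored at day 42 and loses 182 − 42 = 140 of 168 days. A carrier who is negative again at day 182 loses nothing. A child positive at all seven smears has no person-time. Because mITT requires evaluable person-time, that child could leave the primary population.

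**3. How common carriage is.** Protocol 5.2.4, children aged 6 to 10 at the site: of 964 positive smears, "582 (60.4%) occurred without reported symptoms", and 4419 negative visits were symptom-free. So 582/(582 + 4419) = 11.6% of symptom-free visits were smear-positive, pooled over dry and wet seasons.

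**4. Effect on VE.** Simulation with 200,000 children per arm, 168 days and smears every 28 days. Cox VE was computed with event-free children censored at 26 weeks and then at the last negative smear. Assumptions not in the documents: 40% or 70% of infections symptomatic; mean carriage 45 or 120 days; flat or peaked season; no carriers at the start; full attendance.

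| Vaccine effect; control risk; season | Symptomatic share, mean carriage | Event-free children censored early, control / vaccine | VE, 26 weeks → last negative | Kaplan-Meier risk, control; vaccine |
|---|---|---|---|---|
| Infection −50%; 0.35; flat | 0.7, 45 d | 4.6% / 2.3% | 49.6 → 49.9% | 0.349 → 0.353; 0.195 → 0.196 |
| same | 0.7, 120 d | 9.4% / 4.8% | 49.8 → 50.7% | 0.349 → 0.361; 0.194 → 0.198 |
| same | 0.4, 45 d | 15.4% / 8.0% | 49.5 → 50.7% | 0.348 → 0.364; 0.194 → 0.199 |
| same | 0.4, 120 d | 29.4% / 15.8% | 49.9 → 53.1% | 0.349 → 0.394; 0.193 → 0.207 |
| None; 0.35; flat | 0.4, 120 d | 29.0% / 29.2% | −0.2 → −0.3% | 0.349 → 0.394; 0.350 → 0.395 |
| Symptoms only −50%; 0.35; flat | 0.4, 120 d | 29.1% / 36.8% | 50.0 → 46.8% | 0.349 → 0.393; 0.193 → 0.235 |
| Infection −50%; 0.60; peaked | 0.4, 120 d | 50.8% / 30.1% | 49.9 → 54.8% | 0.599 → 0.710; 0.367 → 0.418 |
| Symptoms only −50%; 0.60; peaked | 0.4, 120 d | 50.9% / 61.2% | 50.0 → 41.6% | 0.598 → 0.709; 0.365 → 0.522 |

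Shift in VE over the whole grid:

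- Infection prevented (true VE 40% or 50%): +0.3 to +3.3 points at control risk 0.35, and +0.4 to +4.9 at 0.60.
- Symptoms only: −0.9 to −8.4 points.
- Mixed (infection −25%, symptoms given infection −33%): +0.1 to −2.1 points.
- No effect: within 0.2 points of zero.

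A separate set of infection-blocking runs agrees. The run nearest the planning rate (60% infected, half symptomatic, 60 days' carriage) moved VE from 48.7% to 50.0%. The most extreme (90% infected, 35% symptomatic, 120 days) moved it from 51.1% to 57.3%.

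**5. Against the trial's precision.** The 56.7 events split as 108 × 0.35 = 37.8 and 108 × 0.175 = 18.9. The SE of log HR is √(1/37.8 + 1/18.9) = 0.282. Around HR 0.50 the limits are 0.50 × exp(±1.96 × 0.282) = 0.288 and 0.869, so the 95% interval for VE is about 13% to 71%.

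**The case against.** **The sentence is garbled and may be meant for early leavers only.** That is possible. But early leavers already have the rule in SAP 3.4, so on this reading the clause is redundant. A programmer following the text would apply it to every event-free child. The principle in SAP 3.4, the last date at which the outcome can be determined, would allow a symptom assessment. Its only example ("e.g., date of last available TBS specimen without parasitemia") points back to the smear.

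**A reader might infer that placebo children lose more follow-up and that VE is therefore overstated.** The documents do not establish this. It needs a vaccine effect on carriage. Protocol 3.2.2 supports one, since the earlier field trials in Mali and Burkina Faso measured freedom from parasitaemia and the proposed mechanism acts at the liver stage. However, those were adult trials, and no expected carriage by arm is given for this age group. If the vaccine turned clinical infections into silent ones, the sign would reverse.

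**The size is modest.** This stands. Only event-free children positive or unsmeared at the final smear are affected. The site's 11.6% lies between the rows with 9.4% and 15.4% of event-free controls censored early, where VE moves by 0.9 and 1.2 points. End-of-season carriage could be higher than this year-round average, and artemether-lumefantrine clearance before V1 could lower it. The 60.4% figure is a share of positive smears, not of children. It shows that silent parasitaemia is usual among positives, not that most children carry it. The shifts are small beside an interval of about 13% to 71%, but they are systematic and avoidable.

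**Conclusion.** The rule as written does not fit the symptomatic endpoint. It discards observed, event-free, at-risk time according to a post-randomisation infection, so the censoring is informative.

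Kaplan-Meier risk is inflated in both arms whenever there are carriers: in simulation a control risk of 0.35 became 0.35 to 0.40, and 0.60 became 0.61 to 0.71. This happens even with no vaccine effect.

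VE is generally biased when the vaccine works. The bias is probably upward, by about 0.3 to 5 points (6 in one extreme run), if the vaccine prevents infection. It is downward, by about 1 to 8 points, if the vaccine prevents only symptoms, and close to nil for some mixtures of the two. With no vaccine effect there is no bias, so a reader should not infer that the rule creates a false positive.

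The sizes rest on assumed symptomatic fractions, carriage durations and seasonality. The mismatch between rule and endpoint does not.

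**What to change.** Before unblinding, amend SAP 3.2.1 and Protocol 10.4.3. For both case definitions of Pf malaria with symptoms, censor event-free children at the earlier of 26 weeks after V3 and the last contact at which symptoms were assessed, whatever the smear result. In SAP 3.2.2 and the matching protocol text, state that censoring at the last negative smear applies only to the Pf malaria (parasitaemia) endpoint. Change the example in SAP 3.4 and Protocol 10.4.1 so that it names a symptom assessment for the symptomatic endpoint and a smear for parasitaemia. Censoring at the last negative smear could be reported as a sensitivity analysis.

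The cost is wording and a few lines of programming. The two-weekly contacts are already scheduled, and no new data are needed.

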3.2.2 Secondary: VE against Pf malaria

VE against *Pf malaria* will be assessed as for VE against *Pf malaria with symptoms*, using the mITT population and censoring participants who do not experience the endpoint by 6 months after V3.

The cumulative probability of *Pf malaria* through 26 weeks post V3 will be similarly presented as for *Pf malaria with symptoms*.

3.3 Exploratory Analyses

The trend of the immune response, more specifically the humoral and cellular immune responses, to PfSPZ vaccine will be modelled and compared between the vaccine recipients and the controls. This will be achieved via a generalized linear regression which accounts for the within-subject correlation.

To assess genetic relatedness of the PfSPZ vaccine parasite strain to malaria infection parasites, a genotypic sieve analysis will be performed to analyze the sequences of peripheral blood *Pf* parasites from infected subjects. The sieve analysis targets at differentiating protective efficacy against different genotypes of infection-inducing parasites with genotype defined by the number of mismatches to the PfSPZ footprint.

Recurrent event analysis will be performed to assess vaccine efficacy against all episodes of *Pf malaria with symptoms*, or *Pf malaria*, rather than against the first episode.

To evaluate the impact of detectable parasitemia prior to vaccination on vaccine efficacy, vaccine efficacy may be additionally evaluated via the above mentioned analyses stratified by baseline status of parasitemia.

3.4 Handling of missing Data

It is anticipated that some event dates required for safety analyses may be incomplete. If the event onset day is unknown, then the date will be imputed as the last date the subject could reliably be assumed to be event free (e.g., the previous study visit where the event was not reported). If the resolution day is incomplete, then the date will be imputed as the date that the event was reliably known to no longer be present.

It is anticipated that some TBS results will be missing. In those instances where one TBS is missed, the result will be imputed to be the same as the result of the next TBS. Up to three such single missing TBS will be allowed in a research subject during the 26 weeks of follow-up without disqualifying the participant from the ATP population (as long as the individual meets other requirements for ATP, such as receiving all three immunizations within the correct time windows). If there are situations where two or more consecutive TBS are missed, the result will again be imputed to be the same as the result of the next TBS, and the research subject will be included in the mITT population (as long as the individual meets other requirements for mITT, such as receiving all three immunizations). If the only TBS missed is the last, there will be no imputation, the missing data point will be ignored, and the individual may be included in the ATP population. If the two or more TBS missed are the last, there will be no imputation, the missing data points will be ignored, and the individual may be included in the mITT population. However, if more than the last two TBS are missed, the individual will not be included in proportional efficacy analyses, although may be included in time-to-event efficacy analyses.

Subjects who discontinue early or are lost to follow-up will be censored from applicable analyses at the last date where the study outcome can reliably be determined (e.g., date of last available TBS specimen without parasitemia).

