3. To measure VE using other outcome measures such as against all episodes of *Pf malaria with symptoms* and *Pf malaria* rather than against the first episode, using proportional analysis, or using ITT or ATP populations, or severity of malaria infections or hemoglobin concentration.
4. To explore the relationship between detectable parasitemia prior to vaccination and VE.

Endpoints:

Primary Endpoints:

1. Proportion of vaccinees compared to controls experiencing related SAEs from V1 to 26 weeks after V3
2. VE computed as one minus the estimated hazard ratio (HR) (time-to-event analysis) for first episode of *Pf malaria with symptoms* from 2 weeks after V3 to 26 weeks after V3 in the modified ITT (mITT) population.

Secondary Endpoints:

1. Safety and tolerability in children
 - The differences in proportions of vaccinees compared to controls experiencing unsolicited AEs from the time of V1 to 14 days after V3 (or last immunization).

- The differences in proportions of vaccinees compared to controls experiencing laboratory abnormalities from time of V1 to 14 days after V3.
- The differences in proportions of vaccinees compared to controls experiencing solicited Aes during the 7 days following each immunization.
- 2. VE computed as one minus the estimated hazard ratio (HR) for first episode of *Pf malaria* detected by thick blood smear (TBS), from 2 weeks after V3 to 26 weeks after V3 in the mITT population.
- 3. Antibody levels to PfCSP by standardized ELISA comparing protected and unprotected vaccinees and controls.

Exploratory Endpoints:

- 1. Humoral and cellular immune responses to PfSPZ Vaccine
- 2. Genotyping of peripheral blood Pf parasites
- 3. Additional measures of VE
 - VE against all episodes (rather than first episode) of *Pf malaria with symptoms* and *Pf malaria* by Cox regression analysis
 - VE computed by proportional (binary) analysis (1 – risk ratio) for first episode of *Pf malaria* detected by TBS, from 2 weeks after V3 to 26 weeks after V3 in the intention-to-treat (ITT), mITT and according to protocol (ATP) populations (whole group and subgroups)
 - VE computed as one minus the estimated HR for first episode of *Pf malaria* detected by TBS, from 2 weeks after V3 to 26 weeks after V3 in the ITT and ATP populations (whole group and subgroups)
 - VE for *Pf malaria* measured by and nucleic acid detection in children from 2 weeks after V3 to 26 weeks after V3 using both (time to event, proportional/binary)

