10.4 STATISTICAL ANALYSES

10.4.1 General Approach

Missing Data

Subjects who discontinue early or are lost to follow-up will be censored from applicable analyses at the last date where the study outcome can reliably be determined (e.g., date of last available TBS specimen without parasitemia).

It is anticipated that some event dates required for safety analyses may be incomplete. If the event onset day is unknown, then the date will be imputed as the last date the subject could reliably be assumed to be event free (e.g., the previous study visit where the event was not reported). If the resolution day is incomplete, then the date will be imputed as the date that the event was reliably known to no longer be present.

It is anticipated that some TBS results will be missing. In those instances where one TBS is missed, the result will be imputed to be the same as the result of the next TBS. Up to three such single missing TBS will be allowed in a research subject during the 26 weeks of follow-up without disqualifying the participant from the ATP population (as long as the individual meets other requirements for ATP, such as receiving all three immunizations within the correct time windows). If there are situations where two or more consecutive TBS are missed, the result will again be imputed to be the same as the result of the next TBS, and the research subject will be included in the m-ITT population (as long as the individual meets other requirements for m-ITT, such as receiving all three immunizations). If the only TBS missed is the last, there will be no imputation, the missing data point will be ignored, and the individual may be included in the ATP population. If the two or more TBS missed are the last, there will be no imputation, the missing data points will be ignored, and the individual may be included in the m-ITT population. However, if more than the last two TBS are missed, the individual will not be included in proportional efficacy analyses, although may be included in time-to-event efficacy analyses.

Multiple Testing

The primary VE endpoint is the VE against *Pf malaria with symptoms*. The overall vaccine efficacy will be assessed over all participants.

No multiplicity adjustment will be made for secondary efficacy or safety endpoints.

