3.1 Safety Analyses

The primary safety endpoint is the occurrence of an SAE between V1 and 26 weeks after V3 which is at least possibly related to treatment. Serious AEs which meet this definition will be summarized in frequency tables and listings according to system organ class, preferred term, relatedness, and severity. The primary safety analysis will be performed using the ITT population and according to treatment received at V1, regardless of any randomization or allocation errors. All SAEs will be coded using the Medical Dictionary for Regulatory Activities (MedDRA) and summarized using frequencies, proportions, and exact 95% CIs for proportions. Rates of SAEs (overall and for any system organ class or preferred term with at least 5 events in either group) will be compared using two-sided 0.05 level Fisher's Exact Tests.

Secondary safety endpoints include the occurrence of unsolicited AEs, laboratory abnormalities, and solicited AEs in the ITT population. Unsolicited AEs documented from V1 to 14 days following V3 will be coded using MedDRA and summarized in frequency tables according to system organ class, preferred term, relatedness, and severity. Summaries will be provided overall and according to the vaccination number immediately prior to AE onset. Rates of unsolicited AEs (overall and for any system organ class or preferred term with at least 5 events in either group) will be compared using two-sided 0.05 level Fisher's Exact Tests. Adverse events leading to premature discontinuation from the study will be listed separately. Clinically relevant laboratory abnormalities recorded in the 14 days after V3 will be summarized in frequency tables by type, grade, and clinical relevance.

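### An unknown AE onset day is imputed to a day when the child was event free, so an unsolicited AE absent at V3+14 and first reported at V3+28 is counted in the V1 to V3+14 endpoint

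*SAP*

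**What the plan says.** Protocol 10.4.1 (Missing Data) and SAP 3.4 give one rule in the same terms for an AE whose onset day is not known: "the date will be imputed as the last date the subject could reliably be assumed to be event free". The example given is "the previous study visit where the event was not reported". Both sections expect some event dates needed for the safety analyses to be incomplete, so the rule will be used.

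The secondary safety endpoint in Protocol 2.1 is the difference in proportions of children "experiencing unsolicited AEs from the time of V1 to 14 days after V3 (or last immunization"). The analysis text in SAP 3.1 is worded differently: "Unsolicited AEs documented from V1 to 14 days following V3 will be coded using MedDRA". Protocol 10.4.2 matches SAP 3.1. Both compare unsolicited AE rates between arms by two-sided 0.05-level Fisher's exact tests.

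In the Schedule of Activities (Protocol 2.3, Table 2), visit 16 is Day 43, 14 days after V3, and visit 17 is Day 57, 28 days after V3. Each has a window of ±3 days. Under Protocol 9.11.4, unsolicited AEs go on being recorded after the first week following an injection, so events that begin after V3+14 do reach the database.

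**The concern.** The rule places onset on a date when the event was established to be absent. The earliest possible onset is the following day. In the middle of a window, one day makes no difference. At the end of a window it decides whether the event counts, and here a scheduled visit falls on the last day of the unsolicited-AE window.

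At stake is a between-arm comparison of AE rates. Events that cannot have begun in the window would be added to both blinded arms. They are later illness, not events of the vaccination period, and adding them alike to both arms pulls a rate ratio towards 1. For a safety comparison that is the less cautious direction.

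**Working it through.** **Visit dates.** V3 is Study Day 29. Subtracting it reproduces the printed offsets: 43 − 29 = 14, 57 − 29 = 28, and 211 − 29 = 182 for the final visit.

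**Nominal schedule.** An event absent at V3+14 and first reported at V3+28 began on one of the days V3+15 to V3+28. That is 14 possible days, none of them in a window that ends at V3+14. The rule assigns V3+14, which is inside.

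**Allowing for the visit window.** Let visit 16 fall at V3+L, with visit 17 on V3+28. There are 28 − L possible onset days, of which 14 − L (if positive) are inside the window. For L up to 14, with onset equally likely on each possible day (an assumption), the share of these events that really began outside is 14/(28 − L).

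| Visit 16 at | Date under the plan | Possible onset days inside / total | Share truly outside | Day-after date |
|---|---|---|---|---|
| V3+11 | V3+11, in | 3/17 | 82% | V3+12, in |
| V3+12 | V3+12, in | 2/16 | 88% | V3+13, in |
| V3+13 | V3+13, in | 1/15 | 93% | V3+14, in |
| V3+14 | V3+14, in | 0/14 | 100% | V3+15, out |
| V3+15 to V3+17 | out | none | not imported | out |

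Only the V3+14 row holds an event that is counted although its onset cannot lie in the window. In the three rows above it, onset in the window is possible, and keeping the event is a defensible cautious choice. The day-after rule changes status in the V3+14 row alone. On nominal days the midpoint (V3+21) and the report date (V3+28) would also put the event outside. For an early visit, however, they would drop events that may belong: with L = 11 the midpoint is V3+19.5.

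**Rough size.** The documents give no expected number, so this is an illustration.
- Protocol 5.2.4 reports 382 + 607 = 989 visits with symptoms in 277 local children aged 6 to 10.
- Assuming 15 to 20 months observed per child, that is 989/(277 × 20) = 0.18 to 989/(277 × 15) = 0.24 per child-month.
- For 134 children over 14 days this is about 11 to 15 illnesses per arm.
- If 5% to 20% lack an onset day (assumed), about 0.5 to 3 events per arm are imported when every visit 16 is on its nominal day.
- If visit days were spread evenly over the seven-day window (assumed), one seventh would be on V3+14: 0.55/7 = 0.08 to 2.9/7 = 0.4 events per arm.

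This counts illnesses, whereas the endpoint counts children. A child who already had an AE in the window adds nothing to the overall comparison.

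**Dilution near the upper end.** Take assumed true rates of 20% and 8% for one AE category, with 120 per arm. Let 2% of children in each arm gain an imported event; 3 of 134 is 2.2%. The rates become 1 − 0.80 × 0.98 = 21.6% and 1 − 0.92 × 0.98 = 9.8%. The risk ratio falls from 2.50 to 2.20, and Fisher power from 72% to 65%. Having all imported events fall in one category is an extreme case.

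**The case against.** The best defence is that the rule is pre-specified, identical in both documents, applied alike to both blinded arms, and leans towards counting events close to vaccination. Most of that stands, and no systematic arm imbalance should be expected. But leaning towards inclusion is cautious only while onset in the window is possible. On V3+14 it is not.

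A second defence is that SAP 3.1 and Protocol 10.4.2 count events *documented* in the window. Read by date of record, an event first reported on Day 57 is out and nothing is imported. The endpoint itself speaks of children *experiencing* AEs, which points to onset. The plan should say which reading applies.

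A third is rarity. Protocol 9.11.4 requires time of onset for each AE, contacts in this period are fortnightly, and parents are urged to report illness. An unscheduled contact after V3+14 could also supply a later event-free date. This limits the size but leaves the rule as it is.

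A reader might infer four stronger points. The documents do not support them.
- *The solicited window is affected in the same way, because Day 36 is V3+7.* Protocol 9.11.4 and footnote A of the Schedule of Activities end solicited collection at 7 days. A first report on Day 43 is recorded as unsolicited, and nothing says that an imputed date reclassifies it.
- *Events dated to a dosing day cannot be attributed to a dose.* Summaries are "according to the vaccination number immediately prior to AE onset". Protocol 7.1.2 keeps the child under observation for at least 30 minutes after injection, and 9.3 lists a post-vaccination evaluation. Event free on that day therefore includes time after the dose, and the event goes to that dose.
- *A recorded onset month is ignored.* The standard is the last date the child can reliably be taken as event free; the previous visit is only an example. A known month moves that date forward to at least the last day of the month before.
- *Malaria illness would make the error unequal between arms.* This needs transmission to be under way by about Day 57, an effective vaccine, and malaria episodes that lack onset dates although symptoms prompt a smear. The documents do not establish that combination.

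**Conclusion.** The point holds for one boundary. When the last event-free visit falls exactly on V3+14, the rule counts in the V1 to V3+14 endpoint an unsolicited AE that cannot have begun there, and neither document has an exception or sensitivity analysis that repairs it. If visit 16 is held earlier, onset inside the window remains possible; if later, nothing is imported.

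This assumes that the window includes V3+14 and is applied by onset date. The effect is small: unknown-onset AEs only, in a secondary safety endpoint, with the number resting on assumed missingness. The expected direction is dilution of a between-arm difference. The primary safety endpoint is little affected, since its window closes at the last scheduled visit (V3+182). It is a minor correction, best made before unblinding.

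**What to change.** In SAP 3.4 and Protocol 10.4.1, keep the present standard for finding the last event-free date and add one day: an unknown onset day is set to the day after the most recent date on which the subject was known not to have the event. In SAP 3.1 and Protocol 10.4.2, replace the word *documented* with a statement that the V1 to V3+14 window is applied by onset date, actual or imputed.

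Events whose onset could lie in the window stay in it; only those that cannot belong leave. The change does not resolve the genuine uncertainty when visit 16 is early, and it need not. It costs a sentence in each place and one line of programming, with no new data. The downside is that a few events leave the per-arm counts for this window.
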